6.4 REPORTING PROCEDURES FOR ADVERSE EVENTS

6.4.1 Recording Adverse Events

The Investigator will record all AEs (both AEs and SAEs) considered attributable (relationship of possible, probable, causal relationship) to the study procedure or the ENSEAL X1 or GEN11 devices in the source documents and eCRF.

Standard medical terminology should be used when recording AEs. In addition, the following information should be recorded:

- Onset date;
- Resolution date or date of death;
- Severity of the event;
- Indication of whether the event is serious;
- Relationship of AE to the study devices;
- Relationship of AE to the study procedure;
- Action taken;

- Event status; and
- Was AE anticipated or not (only for SAEs).

Data related to AEs will be collected until the event resolution, or until the event is considered stable, or until all attempts to determine the resolution of the event are exhausted. All AEs that are unresolved at study completion (or at the last visit completed for early withdrawal subjects) will be recorded as ongoing at study end.

6.4.2 Reporting Adverse Events

The Investigator is required to report AEs to the Sponsor within 2 weeks from when the study site becomes aware of the event. All reportable AEs must be reported on the AE eCRF and be documented in a timely manner throughout the study duration.

6.4.3 Reporting Serious Adverse Events

Any reportable AE that the Investigator determines to be a SAE must be reported by the study site within 72 hours of becoming aware of the event to the Sponsor by completing the AE eCRF. A notification containing the pertinent data will be automatically generated by the EDC system and forwarded to the Sponsor. If applicable, supporting SAE documentation should be de-identified and provided to the Clinical Trial Leader. The report of an SAE by a study site does not constitute an admission that study personnel or the user facility (hospital/clinic) caused or contributed to the event. The study site is also responsible for submitting SAEs to the reviewing IRB/EC per their IRB/EC procedures.

7.0 PRODUCT COMPLAINTS

A product complaint is any written, electronic, or oral communication that alleges deficiencies related to the identity, labeling, quality, durability, reliability, safety, effectiveness, or performance of a device after it is released for distribution. A product complaint may or may not be associated with an AE/SAE.

7.1 REPORTING PRODUCT COMPLAINTS FOR MARKETED DEVICES

7.1.1 Reporting of Approved EES Marketed Devices

All product complaints related to devices in the procedure shall be documented throughout the clinical investigation. Product complaints related to an Ethicon-manufactured ENSEAL X1 or GEN11 devices must be reported to the Sponsor in a timely manner and no later than 24 hours after becoming aware of the event. When a sponsor representative becomes aware of a product complaint, the Product Complaint Team must be notified within 24 hours after becoming aware of the event. The Product Complaint Form must be emailed to the Sponsor Customer Complaint team at the following email address:

[contact]

The sites will report Product Complaints by completing the Product Complaint Form. If a product complaint is related to a safety event, the site must complete an AE eCRF as well. One copy of the processed form should be kept on-site and the device should be retained. Sponsor representatives will organize collection of the device for evaluation as needed.

Product complaints will be handled in Japan sites using the Johnson & Johnson K.K (JJKK) Medical Company specific local standard operating procedures for product complaints. The clinical site will report the product complaint to the site monitor within 24 hours. The site monitor will then email to both JJKK Quality Assurance and Japan Clinical Operations Study lead within 24 hours of awareness. JJKK Quality Assurance will submit

the product compliant into the Global Complaint Management Database System within 2 calendar days.

7.1.2 Reporting of Approved Marketed Devices and Commercially Available Devices (not Ethicon)

The site should report Product Complaints of non-Ethicon devices that are approved marketed devices or commercially available medical devices according to the specific product's manufacturer specifications/guidelines.

9	Data Monitoring Committee (DMC)	11
	Appendix: Table Shells and List of Listings to be Generated	11

1 Introduction

This is the Statistical Analysis Plan (SAP) for the final analysis of data collected under Protocol ENG_2020_04. This SAP describes in detail the statistical methodology and statistical analyses for this protocol.

1.1 Study Objectives

The primary objective of this study is to demonstrate the acceptable performance and safety of the ENSEAL X1 and GEN11 devices when used per the instructions for use (IFU).

1.2 Study Design

This prospective, single-arm, multi-center study will collect clinical data in a post-market setting by procedure group (thoracic, urologic, and ENT). Investigators will perform each procedure using the device in compliance with their standard surgical approach and the ENSEAL X1 and GEN11 IFUs. Subjects will be consented and screened anytime during a period of 8 weeks prior to the date of surgery. Subjects will be considered enrolled when the ENSEAL X1 device has been attempted to be used for a vessel transection during thoracic, urologic, or ENT procedures. All enrolled subjects will be followed post-operatively through discharge and again at 28 days (\pm 14 days) post-surgery; therefore, from the surgery date to study exit, the duration will be approximately 6 weeks.

A minimum of 105 subjects enrolled (maximum of 120 subjects enrolled) will be included in the study from up to 12 surgery centers globally with the following procedure targets:

- A minimum of 35 subjects enrolled to a maximum of 40 subjects enrolled for thoracic procedures (e.g., lung resections [branches, no pulmonary artery/pulmonary vein {PA/PV}]).
- A minimum of 35 subjects enrolled to a maximum of 40 subjects enrolled for urologic procedures (e.g., nephrectomy); and
- A minimum of 35 subjects enrolled to a maximum of 40 subjects enrolled for ENT procedures (e.g., thyroidectomy, tonsillectomy, parotidectomy, radical neck).

2 Treatment Assignment

This is a single-arm study where all enrolled subjects will have the ENSEAL X1 device utilized for transection of at least one vessel.

3 Randomization and Blinding Procedures

As this is a single-arm study, no randomization will occur, and no blinding procedures are required.

4 Interval Windows

Interval windows for the purpose of analysis in this study will not be defined outside of those already specified in the protocol for visit scheduling as the collection of data for the primary and secondary performance endpoints occurs intra-operatively. The final visit occurs approximately 4 weeks after surgery, thus no interval windows need to be defined given the absence of long-term follow-up in this study. The Schedule of Events specifies a window of 14 days around the scheduling of the 4-week follow-up visit, and any information entered in the eCRFs at this visit will correspond to the 4-week visit. There will be no assigning of observations to time points outside of the visit to which they are recorded in the eCRFs.

5 Levels of Significance

No hypotheses are specified for this study and no p-values are being calculated, therefore no level of significance is specified. All estimation of endpoints will be performed using 95% confidence intervals.

6 Analysis Sets

The summary of all performance and safety endpoints will be performed on the set of subjects in whom the ENSEAL X1 device is utilized during the surgical procedure. This will be labeled the ENSEAL Analysis Set. This set of subjects will be identified by having at least one entry in the “Vessel Transected” eCRF or by having answered “Yes” to the question “Was ENSEAL X1 used for tissue cutting or dissection?” on the “ENSEAL X1 Usage” eCRF. The summary of all primary and secondary performance endpoints will be performed by procedure group (thoracic, urologic, and ENT) and on the entire pooled set of subjects. The safety endpoints will be summarized by procedure group and for the entire pooled set of subjects.

7 Sample Size Justification

A sample size of 105 to 120 treated subjects is planned for enrollment in this study. No formal hypothesis is being tested in this study; thus, the sample size was not statistically sized, but rather is considered sufficient for a descriptive summary of performance endpoints within each procedure group. It is expected that at least 1 vessel will be transected within each procedure, providing an expected minimum of at least 35 transections within each procedure group for a total of at least 105 transections.

From a safety perspective on the pooled analysis of 105 subjects and in consideration of rare AEs that may occur (e.g., bleeding requiring blood product transfusion), for an event that has an incidence rate of, for example, 2%, then in a sample of 105 subjects, the probability of observing at least 1 event is 88.0% under a binomial probability model. Thus, this sample size provides a high probability of observing an AE if they do occur and provides reasonable assurance to conclude that

the likelihood of such AEs is less than 3.5% if they do not occur based on the upper limit of an exact 95% confidence interval when 0 events out of 105 subjects are observed.

8 Analyses to be Conducted

8.1 General Conventions

Subject data will be summarized in tables and further details will be provided in listing. All eCRF data will be listed per subject for all subjects. Descriptive statistical analyses will be provided for pre-specified study endpoints. Summaries for continuous variables will include number of observations (n), mean, standard deviation, median, minimum, and maximum. Summaries for categorical variables will include total and counts for each category and their corresponding percentages.

Analyses will be conducted using SAS software. During the course of programming of tables that are mocked up in this SAP, minor modifications may become necessary. Examples of these minor modifications include, but are not limited to, re-wording of a footnote, addition of a footnote, re-labeling of a column, or addition or removal of a column from a table or listing. In cases where modifications to tables or listings are not related to a change in statistical analysis methodology or conclusions that could be made on the originally proposed methodology, then no amendment of the SAP is necessary. Any final analyses that differ from what has been specified in this document will be identified within the final statistical output and documented within the clinical study report.

8.2 Disposition of Study Subjects

Subject disposition will be summarized by procedure group (thoracic, urologic, and ENT) and in total using counts and percentages. The number and percentage of subjects in the ENSEAL Analysis Set who completed, screen failure and discontinued will be tabulated along with the specific reasons for discontinuation.

8.3 Demographic, Baseline, and Surgical Characteristics

Summary statistics of subject demographics (age, sex, childbearing potential, race, and ethnicity) and vital signs (height, weight, and body mass index) will be presented by procedure group and in total. Background information (primary indication, specific procedure performed, smoking history, and cancer history) will be summarized in a similar manner. Medical history will be summarized by Medical Dictionary for Regulatory Activities (MedDRA) system organ class and preferred term. Surgical characteristics including, at minimum, procedure duration, occurrence of vessel skeletonization, presence of inflamed tissue or calcified tissues/vessels, volume of estimated intra-operative blood loss, and use of ENSEAL X1 for tissue cutting or dissection will be summarized by procedure group and in total.

8.4 Primary and Secondary Endpoints and Associated Hypotheses

No formal hypotheses are specified for the primary and secondary endpoints of this study. The study endpoints are representative of endpoints that are currently reported in the available literature for similar energy devices, and this will allow for comparisons with the results from this study.

8.4.1 Primary Endpoint and Associated Hypotheses

No formal hypotheses are specified for the primary endpoint of this study.

The primary performance endpoint in this study is the number and percentage of vessels where hemostasis (\leq Grade 3) is achieved using the ENSEAL X1 device. The hemostasis grading scale is defined as:

- Grade 1: no bleeding at transection site;
- Grade 2: minor bleeding at transection site, no intervention needed;
- Grade 3: minor bleeding at transection site, mild intervention needed, use of compression, basic energy devices (monopolar and/or bipolar device), and/or touch-ups with ENSEAL X1.
- Grade 4: significant bleeding (e.g., pulsatile blood flow, venous pooling) requiring intervention such as extensive coagulation or use of additional hemostatic measures (e.g., hemoclips, staples, sutures, fibrin sealants, other advanced energy products).

The primary performance endpoint will be summarized at the vessel transection level as multiple vessel transections per subject are expected; that is, the denominator for the primary endpoint will be the total number of vessel transections and the numerator will be the number of vessel transections where hemostasis (\leq Grade 3) is achieved. An exact 95% confidence interval using the Clopper-Pearson method will be estimated. The statistics for the primary performance endpoint will be presented by procedure group and in total.

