3.0 INVESTIGATIONAL PLAN

3.1 OVERALL STUDY DESIGN AND PLAN - DESCRIPTION

This prospective, single-arm, multi-center study will collect clinical data in a post-market setting by procedure group (thoracic, urologic, and ENT). Investigators will perform each procedure using the device in compliance with their standard surgical approach and the ENSEAL X1 and GEN11 IFUs.

Subjects will be consented and screened anytime during a period of 8 weeks prior to the date of surgery. Subjects will be considered enrolled when the ENSEAL X1 device has been attempted to be used for a vessel transection during thoracic, urologic, or ENT procedures. All subjects enrolled will be followed post-operatively through discharge and again at 28 days (\pm 14 days) post-surgery; therefore, from the surgery date to study exit, the duration will be approximately 6 weeks.

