3.2.2 Screening Failures

All subjects signing consent who do not have at least one vessel transection attempted by ENSEAL X1 during their procedures will be recorded as screen failures. For subjects who are determined to be screen failures, only the relevant eCRF pages (inclusion/exclusion criteria, demographics, AEs, subject completion/discontinuation) will be completed.

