3.4.2 Surgical Variables

The following variables will be recorded preoperatively, intraoperatively, or postoperatively:

- Date/time of hospital admission;
- Body weight (kg or lbs; no shoes);
- Body height (cm or in; no shoes);
- Procedure duration, defined as first skin incision to final skin closure;
- Did vessel skeletonization occur (Yes/No; if Yes, describe vessel skeletonized and device used)?;
- Was there presence of inflamed tissue, calcified tissues/vessels, atherosclerotic tissue, fibrotic tissue, or presence of adhesions intraoperatively, if applicable (Yes/No; if Yes, describe the tissue along with location)?;
- Were adhesions removed or divided by ENSEAL X1 (Yes/No; if Yes, describe adhesions along with location and complete 5-point scale)?;
- Were lymphatics and tissue bundles divided by ENSEAL X1 (Yes/No; if Yes, describe lymphatics and tissue bundles along with location and complete 5-point scale)?;
- Was ENSEAL X1 used for grasping tissue, tissue cutting, or tissue dissection (Yes/No; if Yes, describe activity along with location and complete 5-point scale)?;

- Conversion to open with reason, if applicable;
- Volume of estimated intra-operative blood loss;
- Use of any other energy device (monopolar, traditional bipolar, advanced bipolar, ultrasonic) in primary procedure (type, name, and number of device and reason for use), if applicable;
- Name, product code, and number of Ethicon trocars used with ENSEAL X1; if applicable;
- Type and name of trocar used with ENSEAL X1 device, if applicable;
- Was there prophylactic use of clips as standard of surgical care before vessel transection (Yes/No; if Yes, name vessel transected, and number of clips prophylactically applied);
- For each vessel transected with ENSEAL X1:
 - Name of each vessel;
 - Hemostasis grading scale assessment (1-4);
 - Surgeon determination of diameter size range (< 3 mm, 3 to 5 mm, and > 5 to 7 mm);
 - Image captured where the vessel is perpendicular and below the open jaw of the ENSEAL X1 device;
 - For every Grade 3 vessel transection:
 - Compression used as a mild intervention, if applicable (Yes/No);
 - Touch-ups with a monopolar device, if applicable (Yes/No; if Yes, record number of touch-ups);
 - Touch-ups with a bipolar device, if applicable (Yes/No; if Yes, record number of touch-ups);
 - Touch-ups with ENSEAL X1 (Yes/No; if Yes, record number of touch-ups);
 - For every Grade 4 vessel transection intervention:

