8.7 Handling of Missing Data

All summaries will be performed for enrolled subjects only and with observed data. There will be no imputation of data for early terminated subjects or for missing data within the database.

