Median (Min, Max)	xx.x (xx, xx)	xx.x (xx, xx)	xx.x (xx, xx)	xx.x (xx, xx)

Grade 3 Vessels Using Bipolar Touch-ups [3]

xx (xx.x)	xx (xx.x)	xx (xx.x)	xx (xx.x)
-----------	-----------	-----------	-----------

Number of Touch-up of Grade 3 Vessels Using Bipolar Device [3]

N	xx	xx	xx	xx
Mean (SD)	xx.x (xx.x)	xx.x (xx.x)	xx.x (xx.x)	xx.x (xx.x)
Median (Min, Max)	xx.x (xx, xx)	xx.x (xx, xx)	xx.x (xx, xx)	xx.x (xx, xx)

Grade 3 Vessels Using ENSEAL X1 Touch-up [3]

xx (xx.x)	xx (xx.x)	xx (xx.x)	xx (xx.x)
-----------	-----------	-----------	-----------

Number of ENSEAL X1 Touch-ups of Grade 3 Vessels [3]

N	xx	xx	xx	xx
Mean (SD)	xx.x (xx.x)	xx.x (xx.x)	xx.x (xx.x)	xx.x (xx.x)
Median (Min, Max)	xx.x (xx, xx)	xx.x (xx, xx)	xx.x (xx, xx)	xx.x (xx, xx)

Vessels transected as Grade 4 [4]

xx (xx.x)	xx (xx.x)	xx (xx.x)	xx (xx.x)
-----------	-----------	-----------	-----------

Name of Vessel Transected as Grade 4 [4]

Name 1	xx (xx.x)	xx (xx.x)	xx (xx.x)	xx (xx.x)
Name 2	xx (xx.x)	xx (xx.x)	xx (xx.x)	xx (xx.x)
Name 3	xx (xx.x)	xx (xx.x)	xx (xx.x)	xx (xx.x)
...				

Number of Additional Hemostatic Measure Used to Obtain Hemostasis for

Grade 4 Vessels [4]

N	xx	xx	xx	xx
Mean (SD)	xx.x (xx.x)	xx.x (xx.x)	xx.x (xx.x)	xx.x (xx.x)
Median (Min, Max)	xx.x (xx, xx)	xx.x (xx, xx)	xx.x (xx, xx)	xx.x (xx, xx)

Type of additional hemostatic measure(s) used to obtain hemostasis for

Grade 4 Vessels [2]

Hemoclips	xx (xx.x)	xx (xx.x)	xx (xx.x)	xx (xx.x)
Staples	xx (xx.x)	xx (xx.x)	xx (xx.x)	xx (xx.x)
Sutures	xx (xx.x)	xx (xx.x)	xx (xx.x)	xx (xx.x)
Fibrin Sealants	xx (xx.x)	xx (xx.x)	xx (xx.x)	xx (xx.x)
Adjuactive Topical Hemostats (except Fibrin Sealants)	xx (xx.x)	xx (xx.x)	xx (xx.x)	xx (xx.x)
Other advanced energy products	xx (xx.x)	xx (xx.x)	xx (xx.x)	xx (xx.x)
Other	xx (xx.x)	xx (xx.x)	xx (xx.x)	xx (xx.x)

1 Denominator and percentages are based on number of vessels transected in each group.

2 Multiple responses are collected

3 The denominator is number of Grade 3 vessel transections

4 The denominator is number of Grade 4 vessel transections

Programming notes:

1. Only records indicated as “Original procedure” will be summarized in this table.
2. For number of vessels using touch up questions, the number presented will be the number of times “yes” is answered to the corresponding CRF question (VTMONO or VTENS); For summary statistics on number of touch-ups, the variables VTTUP and VTTUPS will be summarized

The following tables will have the same format as Table 9:

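### Enrolment counts attempted ENSEAL X1 transections but the primary rate counts only vessels transected, so unfinished attempts can drop out and the reported hemostasis rate can be too high

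*SAP*

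**What the plan says.** **Entry is by attempt.** Protocol 3.1 and SAP 1.2: "Subjects will be considered enrolled when the ENSEAL X1 device has been attempted to be used for a vessel transection". Protocol 3.2.2 is the mirror image; the screen failures are "All subjects signing consent who do not have at least one vessel transection attempted by ENSEAL X1". A subject whose only attempt failed is therefore enrolled.

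**Measurement is by transection.** Protocol 3.4.2 lists the hemostasis grade among the items recorded "For each vessel transected with ENSEAL X1". SAP 8.4.1 sets the denominator: "the denominator for the primary endpoint will be the total number of vessel transections". The footnote to Table 9 agrees: "Denominator and percentages are based on number of vessels transected in each group".

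**The analysis set follows the transection form.** SAP 6: "This set of subjects will be identified by having at least one entry in the" Vessel Transected eCRF, or by a Yes to use of X1 for tissue cutting or dissection. An attempt alone does not qualify.

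**The two are treated as the same.** SAP 2, in words shared with Protocol 5.2, says that "all enrolled subjects will have the ENSEAL X1 device utilized for transection of at least one vessel".

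**Nothing is filled in.** SAP 8.7: "All summaries will be performed for enrolled subjects only and with observed data", with no imputation.

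**The concern.** Suppose X1 is applied to a vessel, the seal or cut cannot be completed, and the surgeon divides the vessel with a stapler, clips or another energy device without significant bleeding. The subject is enrolled. The vessel was not transected with X1, so on a plain reading of Protocol 3.4.2 it gets no grade. The scale does not clearly catch it either: the grades describe bleeding at a transection site, and Grade 4 requires significant bleeding. The vessel then enters neither numerator nor denominator.

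The stated objective is to demonstrate acceptable performance of X1 and GEN11, and SAP 8.4 intends the results for comparison with the literature. A rate conditional on the device having completed its task can miss one kind of performance failure. This also applies to subjects with several vessels, who stay in the analysis set because another vessel was transected.

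There is a safety side as well. A subject with only a failed attempt and no tissue cutting or dissection falls outside the ENSEAL Analysis Set, on which the adverse event tables (Tables 14 to 19) are built. The subject's events would appear only in the listing for all subjects.

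**Working it through.** **1. The plan's own figures.** The only sample-size figures concern safety, and they reproduce.

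- At least one event at 2% incidence in 105 subjects: 1 − 0.98^105 = 0.880, stated as 88.0%.
- Exact two-sided 95% upper limit for 0/105: 1 − 0.025^(1/105) = 3.45%, stated as less than 3.5%.

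Neither bears on this point. The plan gives no expected hemostasis rate and no count of unfinished attempts.

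**2. What happens to an unfinished attempt under the stated rules.**

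| Situation | Enrolled? | In ENSEAL Analysis Set? | Vessel in primary denominator? |
|---|---|---|---|
| Attempt unfinished, another vessel transected with X1 | Yes | Yes | Not on a plain reading |
| Attempt unfinished, no vessel transected, X1 used for cutting or dissection | Yes | Yes | Not on a plain reading |
| Attempt unfinished, no vessel transected, no cutting or dissection | Yes | No | No |
| Attempt bled significantly and was rescued | Yes | If entered on the form | Possibly, as Grade 4 |

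The third row contradicts the sentence in SAP 2 and Protocol 5.2.

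**3. Size, under stated assumptions.** Let c be vessels transected, s those at Grade 3 or lower, and k unfinished attempts that go ungraded. The plan reports s/c. Counting every unfinished attempt as not achieved gives s/(c + k). Intervals are Clopper-Pearson 95%, as in SAP 8.4.1. The values of k, the number of Grade 4 vessels and the total of 300 vessels are assumptions; 105 and 35 are the planned minimum numbers of transections.

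| Setting | Plan: s/c | k = 1 | k = 3 | k = 5 |
|---|---|---|---|---|
| 105 vessels, 2 Grade 4 | 103/105 = 98.1% (93.3 to 99.8) | 103/106 = 97.2% (92.0 to 99.4) | 103/108 = 95.4% (89.5 to 98.5) | 103/110 = 93.6% (87.3 to 97.4) |
| 300 vessels, 6 Grade 4 | 294/300 = 98.0% (95.7 to 99.3) | 294/301 = 97.7% (95.3 to 99.1) | 294/303 = 97.0% (94.4 to 98.6) | 294/305 = 96.4% (93.6 to 98.2) |

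In one procedure group of 35 vessels with no Grade 4, the plan reports 35/35 = 100% (90.0 to 100). With k = 2 this becomes 35/37 = 94.6% (81.8 to 99.3).

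**4. The other end of the range.** If all 3 unfinished attempts had in fact been hemostatic, the attempted-vessel rate would be (103 + 3)/(105 + 3) = 106/108 = 98.1%, the same as the plan's figure to one decimal. With k = 0 there is no difference at all.

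**The case against.** A reader might infer that the hemostasis rate is inflated as a matter of fact. The documents do not support that. They nowhere say that failed attempts are excluded, and they do not define a vessel transection. Inflation requires that unfinished attempts occur, that sites leave them off the vessel form, and that they were failures. An attempt that bled significantly and was rescued fits Grade 4 and may well be entered so.

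A reader might also infer that the bias can only favour the device. That too goes further than the text. X1 has separate seal and cut functions. A vessel sealed by X1 and divided by another instrument without bleeding is not a hemostasis failure, and omitting it removes a success. Scoring every unfinished attempt as not achieved turns the endpoint into a composite of hemostasis and completion, which is not the endpoint in Protocol 2.1. This is a good reason not to replace the primary denominator.

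Nor do such failures vanish from the outputs. Table 12 tabulates generator alarms, SAP 8.4.3 covers other energy devices with the reason for use, and all eCRF data are listed. But none of these planned summaries ties a malfunction to a vessel. Table 8 shows only use and type of other energy devices, and product complaints have no SAP table or named listing.

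Finally, existing records cannot reliably reveal an abandoned attempt in a subject with another transected vessel. Reason for use is recorded for other energy devices and does not extend to staplers, clips or sutures. This limits what can be recovered and must be stated with any count. What remains is the mismatch of definitions and the lack of any rule for unfinished attempts.

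**Conclusion.** The point holds as a gap in definition with a possible, mainly upward, effect on the primary rate. Enrolment is by attempt, grading and the denominator are by transection, and no rule covers the vessels in between. If unfinished attempts occur, go ungraded and count as failures, the first one lowers the rate by about 1 percentage point at 105 vessels, and 3 of them lower it by about 1 point at 300 vessels. The lower end of the range is no change. SAP 8.4.1 expects several transections per subject, so the figures for 105 vessels are near the upper end for a given number of unfinished attempts.

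The study has no hypothesis, threshold or p-value. The effect is on a descriptive estimate and its comparison with the literature, not on a decision rule. Separately, and without any assumption about rates, the statement in SAP 2 and Protocol 5.2 does not follow from the enrolment rule, and SAP 6 can drop an enrolled subject from the safety tables.

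**What to change.** - **Primary analysis:** keep the per-transection rate as primary, for comparability with the literature.
- **SAP 8.8 and Table 9:** add a sensitivity rate per attempted vessel, counting unfinished attempts as not achieved, and a row with the number of unfinished attempts by procedure group.
- **Identification:** at minimum, take enrolled subjects with no Vessel Transected entry. Where the form can still be changed, add a completion-status item for each vessel. Label any count drawn from reason-for-use or product complaint records as possibly incomplete.
- **SAP 6:** define the ENSEAL Analysis Set to include all enrolled subjects, meaning all with an attempted transection, so that they stay in the safety tables.
- **SAP 2 and Protocol 5.2:** replace the wording that X1 is utilized for transection with wording that a transection is attempted.

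The cost is some SAP and protocol wording, two table rows, a form item if still feasible, and slightly more data review. The sensitivity figure may be less favourable than the primary one. No new subjects or visits are needed.
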